4.1. Sample Size

The sample size for Part 1 of the study was selected empirically for an initial evaluation of safety in subjects with COVID-19.

The sample size for Part 2 of the study was determined by simulations based on the following assumptions:

- The time to fecal viral clearance has an exponential distribution for each treatment arm.
- The median time to fecal viral clearance is anticipated to be approximately 21 days for placebo arm and 10 days for niclosamide arm.
- Fecal viral clearance assessments are performed at Day 3, 7, 14, 28, 42 after first dose.
- Log-rank test (2-sided) is conducted to compare treatment difference.

Using a 1:1 randomization ratio, a sample size of 30 patients per treatment arm (60 patients total with a positive stool test for SARS-CoV-2 on Day 1) provides 74% power to detect a significant treatment difference for alpha=0.05 and 83% power for alpha=0.10. It is expected that approximately 40% of COVID-19 patients will be positive for SARS-CoV-2 in the stool sample. Therefore, approximately 150 patients with COVID-19 are needed to be enrolled/randomized to ensure 60 patients have a positive stool test for SARS-CoV-2 on Day 1.

To assess the sensitivity analysis of the above power calculation, additional scenarios of assumptions of stool positivity rate and longer time to fecal viral clearance for niclosamide arm (i.e. less treatment effect) are also evaluated in the below table.

Total Sample Size for Enrollment	Stool Positivity Rate	Niclosamide: Median Time to Fecal Clearance in Days	Placebo: Median Time to Fecal Clearance in Days	2-sided Significance Level (Alpha)	Statistical Power (%)
150	0.3	10	21	0.05	61
150	0.4	10	21	0.05	74
150	0.5	10	21	0.05	84
150	0.3	12	21	0.05	40
150	0.4	12	21	0.05	49
150	0.5	12	21	0.05	61

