5.2 Background and Rationale Update

The original protocol was prepared and submitted about one year ago (August 2020). The overall rationale and objective for targeting acute GI infection with SARS-CoV-2 remains the same. The compelling set of epidemiological studies referenced in the Section below confirm that GI infection with SARS-CoV-2 remains an important COVID-19 clinical problem that deserves focused attention with a gut targeted pharmacologic agent, such as niclosamide. However, it has become apparent that the original design of the clinical trial is too restrictive. The use of overt clinical diarrhea coupled with a positive respiratory swab positive for SARS-CoV-2, which was the original plan, is likely to only capture a subset of the acute cases of GI infection.

The overall incidence of positive stool samples for SARS-CoV-2 is best estimated from two large meta-analyses. These reported that 43% ([Wong et al., 2020](#)) and 43% ([van Dorn et al., 2020](#)) of patients had stool specimens positive for virus. These reports included thousands of patients who were screened from multiple hospital centers. Wong et al., 2020 reported that among the patients with positive stool samples, only 77% reported overt GI symptoms. In separate smaller studies, prospective screening of stool specimens for SARS-CoV-2 detected virus in 55% of patients with positive respiratory disease ([Wu et al., 2020](#)) and 67% of patients with respiratory disease ([Chen et al., 2020](#)). In the latter report only 19% of patients presented with GI symptoms.

Important learnings from these reports are that: 1. In patients with SARS-CoV-2 infection of the GI tract, overt clinical signs and symptoms of GI infection, including diarrhea, are present in only a fraction of the cases. Thus, enrolling patients for treatment of GI infection based solely on diarrhea will miss a majority of infected patients; 2. In every study in which prospective monitoring of stool cultures was conducted, the presence of virus in stool lasted considerably longer than it lasted in the respiratory tract. In some cases, virus was detected in stool over one month after the respiratory episode was resolved. A reservoir of virus likely remained silently in the gut, without persistence of GI symptoms. It is also currently unknown if the GI infection results in prolonging the course and spread of the infection.

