Active viral replication was observed for SARS-CoV in biopsies obtained via colonoscopy up to 10 weeks after the onset of symptoms of both small and large intestine (Leung et al., 2003). This observation fits with staining of viral nucleocapsid protein of SARS-CoV-2 visualized in the cytoplasm of the GI epithelium of patients who tested positive to viral RNA in the feces,

suggesting that the continuous positive detection of viral RNA in the feces results from secretion of the nucleic acid from infected intestinal cells (Xiao et al., 2020).

In an already mentioned meta-analysis (Section 5.3), the pooled prevalence of stool samples positive for virus RNA after hospitalization was 48.1% (95% CI: 38.3% to 57.9%) (Cheung et al., 2020). Similar data are also confirmed from other epidemiological reviews or cross-sectional studies (Tian et al., 2020; Lei et al., 2020). Remarkably, 1 study demonstrated that 70.3% (95% CI: 49.6% to 85.1%) of positive GI samples were collected after virus clearance from respiratory specimens and up to 33 days from the onset of the illness (Cheung et al., 2020). Moreover, stool viral clearance is significantly delayed ($p < 0.001$) in patients treated with steroids compared to patients not taking steroids, with mean clearance time of 20 days versus 11 days (Ling et al., 2020). These conclusions are supported by other studies (Xiao et al., 2020) and reports characterizing the disease specifically in children (Tang et al., 2020).

In a sample of 59 patients with COVID-19 in Hong Kong, the median fecal viral load was 5.1 log₁₀ copies per mL in patients with diarrhea versus 3.9 log₁₀ cpm in patients without diarrhea ($p = 0.06$) (Cheung et al., 2020). Similar values were reported in a European study that documented positive detection of SARS-CoV-2 in stools, with viral load of 6.8 and 8.1 log₁₀ copies per gram of stool in 2 patients (Lescure et al., 2020).

Irrespective of whether the intestine is the primary site of infection or acts as a reservoir for viral replication, the intestine appears to be important in the pathogenesis of SARS-CoV-2.

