12.4 Analysis of Efficacy Variables

The primary endpoint for Part 2, as well as the key secondary efficacy endpoint for Part 1, will be the time from first drug administration to the first fecal RT-qPCR sample negative for SARS-CoV-2 as defined as a quantitative test either below the limit of quantification or above a number of cycles equivalent to a limit of quantification. Secondary efficacy endpoints for Part 1 and Part 2 will be analysed separately.

The primary analysis of the study will be a stratified log-rank test. Stratification will be based on strata defined for randomization. Kaplan-Meier curve figures with 95% CIs will be generated for the total population by treatment and for each stratum by treatment. Tables will present summary statistics of fraction of subjects not cleared by planned visit, and these summary tables will illustrate the total population and each stratum by treatment. Listings of all patients and the time to the primary endpoint along with stratum levels and clarifications required for sensitivity analyses will be generated.

Secondary and exploratory endpoints, along with safety and baseline characteristics, will be summarized with tables, figures, and listings appropriate for each measure.

Full details for all analyses will be provided in the SAP.

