4.3.2. Efficacy Evaluable (EE) Set

The efficacy evaluable (EE) set will consist of all randomized subjects who received at least one dose of study drug, had a positive stool test for SARS-CoV-2 on Day 1 assessed by RT-PCR, and did not test positive for bacteria or parasites in the screening stool analysis by the local laboratory. The EE set will be used for the primary efficacy endpoint and relevant gastrointestinal efficacy secondary endpoints and will be analyzed according to the study treatment as randomized.

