8.1.1. Primary Analysis

The analysis of the primary efficacy endpoint, time to fecal viral RNA clearance, will be conducted on the EE set.

The number and percentages of subjects achieving and not achieving the first fecal viral RNA clearance will be summarized up to each post-first dose study visit (Days 4, 8, 15, 22, 29, 36, and 43) by treatment group. For each study visit, only subjects with available assessment at the visit or having a negative stool test before the visit will be included in the summary and counted in the denominator for the percentages.

A stratified log-rank test will be used to compare time to fecal viral RNA clearance between niclosamide and placebo treatment groups adjusting for stratification factors, age (<65 years or ≥65 years) and sex (female or male). The two-sided p-value will be reported. The estimate of the hazard ratio (niclosamide vs. placebo) and the associated 95% confidence interval (CI) will be obtained from a Cox Proportional Hazards model adjusting for stratification factors and will also be reported.

Kaplan-Meier curves with 95% CIs will be generated for the total population by treatment group. Summary statistics obtained from Kaplan-Meier estimates, including the median time to fecal viral clearance with corresponding 95% CI and the proportion of subjects achieving fecal viral clearance at 3, 7, 14, 21, 28, 35, and 42 days post first dose (Day 1), will be summarized by treatment group.

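### The stated 74% power (83% at alpha 0.10) is for an unstratified log-rank test; the planned stratified test has about 69–70% (about 80%) with the same 60 patients

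*SAP*

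**What the plan says.** The sample-size assumptions in SAP 4.1 are repeated in Protocol 12.2 and the protocol synopsis. They are exponential clearance times, medians of 21 days (placebo) and 10 days (niclosamide), and assessments at 3, 7, 14, 28 and 42 days after first dose. The test is given as: "Log-rank test (2-sided) is conducted to compare treatment difference". On that basis 30 stool-positive patients per arm "provides 74% power to detect a significant treatment difference for alpha=0.05 and 83% power for alpha=0.10". The SAP adds six sensitivity rows for 150 enrolled, varying stool positivity (0.3, 0.4, 0.5) and the niclosamide median (10 or 12 days).

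The analysis sections name a different test. SAP 8.1.1: "A stratified log-rank test will be used to compare time to fecal viral RNA clearance between niclosamide and placebo treatment groups", adjusting for age (<65, ≥65) and sex. Protocol 12.4: "The primary analysis of the study will be a stratified log-rank test. Stratification will be based on strata defined for randomization". SAP section 4 sets the primary test at two-sided 0.05.

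On numbers, SAP 4.1 says "approximately 150 patients with COVID-19 are needed to be enrolled/randomized to ensure 60 patients have a positive stool test". The primary analysis uses the Efficacy Evaluable (EE) set. SAP 4.3.2 also requires that its members "did not test positive for bacteria or parasites in the screening stool analysis by the local laboratory".

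**The concern.** SAP 4.1 is where a reader judges whether 150 patients are enough and how much weight a null result can bear. Its power should therefore be that of the test and analysis set that will be used. Splitting about 60 patients into four strata costs information when the strata carry no prognostic difference, and the plan assumes none. If 20% are aged ≥65 and half are women, the expected stratum sizes are 24, 24, 6 and 6. A stratum of 6 soon has only one arm left at risk, and from then on it contributes nothing. Neither document mentions this cost.

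Two smaller points arise in the same paragraph. The calculation 150 × 0.40 = 60 allows for no EE exclusions for bacteria or parasites. And 60 is an expected count, which enrolling 150 does not guarantee.

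**Working it through.** **Inputs.** From SAP 4.1: medians 21 and 10 days, the five visit times, 30 per arm, and alpha 0.05 and 0.10 two-sided. From SAP 4.2: strata of age (<65, ≥65) by sex. Assumed, because the documents do not give them: 50% female, and 10% to 50% aged ≥65.

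**Method.** Clearance is recorded at the first visit after the simulated time, with censoring at day 42. The statistic is Z = Σ(O − E) / √ΣV, with E = d·n₁/n and V = d·(n₁/n)(n₀/n)(n − d)/(n − 1). The sums run over visits for the plain test, and over visits within strata for the stratified test.

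**1. The plan's figure by formula.** Expected clearances by day 42 = 30 × [(1 − 2^(−42/10)) + (1 − 2^(−42/21))] = 30 × (0.9456 + 0.75) = 50.9. Schoenfeld: √50.9 × ln(2.1)/2 − 1.96 = 0.69, giving 75.4% (84.2% at alpha 0.10). Freedman gives 71.6% (81.2%). The stated 74% and 83% lie between them.

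**2. By simulation, 60 patients** (60,000 trials per setting):

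| Test | Five visits, α 0.05 | Five visits, α 0.10 | Seven visits, α 0.05 |
|---|---|---|---|
| Unstratified | 73.2–73.6% | 82.8–83.0% | 74.2–74.6% |
| Stratified | 69.0–69.8% | 79.4–80.2% | 69.3–70.9% |

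Seven visits is the actual sampling schedule. A second simulation on five visits, with 200,000 trials per strata mix, gives 73.4–73.5% unstratified and 69.1–70.0% stratified. With no treatment effect the stratified test rejects 5.0–5.1% of the time, so the loss is not a calibration artefact.

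**3. Does balance rescue it?** Stool results are not used at randomization, so balance within strata among the positives is not assured. With full balance the stratified test reaches 70.9% (five visits) or 71.7% (seven).

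**4. Patients needed.** The stratified test at 66 patients has 74.1% (five visits) or 74.8% (seven). 66/150 = 44% positivity with no exclusions; 66/(150 × 0.9) = 49% with 10% excluded.

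**5. Sensitivity table:**

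| Positivity, niclosamide median | Stated | Unstratified, recomputed | Stratified | Loss from stratifying |
|---|---|---|---|---|
| 0.3, 10 d | 61 | 60.6 | 55–56 | about 5 |
| 0.4, 10 d | 74 | 73.6 | 69–70 | about 4 |
| 0.5, 10 d | 84 | 82.8 | 80 | about 3 |
| 0.3, 12 d | 40 | 38.5 | 35–36 | about 3 |
| 0.4, 12 d | 49 | 48.9 | 45–46 | about 3 |
| 0.5, 12 d | 61 | 58.3 | 55–56 | about 3 |

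The last column is the recomputed unstratified value minus the stratified one. In the third, fourth and sixth rows, part of the distance from the stated figure is a reproduction gap of 1.2, 1.5 and 2.7 points. The SAP gives no replicate count, so that gap may be simulation error.

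**6. EE exclusions.** The documents give no rate, so these are assumed scenarios. Stratified power for 150 randomized (assumed blocks of 4, random number positive):

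| Positivity | 0% excluded | 5% | 10% | 20% |
|---|---|---|---|---|
| 40% | 70 | 67 | 64–65 | 58–59 |
| 43% | 73–74 | 70–71 | 68–69 | 63 |
| 48.1% | 78–79 | 76 | 73–74 | 68 |

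**7. Number positive.** For a binomial with n = 150 and p = 0.40, P(at least 60) = 0.53; the 5th to 95th percentiles are 50 to 70.

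**The case against.** The SAP lists its simulation test openly and never claims that the 74% belongs to the stratified test. Sizing a trial on a simpler test is a familiar approximation. That the simulation was unstratified is an inference: the listed test carries no strata, and only the unstratified version reproduces 74% and 83%. This bears on how the fault is described. It does not change the fact that the planned test has less power than the figure given.

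The replacement figure needs a strata mix that the documents do not supply. That is true, but the result moves little for 10% to 50% aged ≥65. If almost nobody were ≥65, leaving in effect two strata, stratified power would be about 71.6%. Stratifying can also help when age matters: with an assumed age rate ratio of 0.5 it was slightly better than the plain test, but both fell below 74%. Across the assumed age and sex effects, stratified power stayed at about 66% to 70.5%. This is no argument against stratifying.

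The strongest point is that 40% positivity is cautious. Protocol 5.2 says "The overall incidence of positive stool samples for SARS-CoV-2 is best estimated from two large meta-analyses", both reporting 43%, and cites 55% and 67% from smaller studies. Protocol 5.4 reports that "the pooled prevalence of stool samples positive for virus RNA after hospitalization was 48.1"%. At 43% with no exclusions, stratified power for 150 randomized is 73–74%. The trial's real power may therefore be close to 74%, but the SAP states that figure for 60 patients.

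The existing 0.3 row (45 patients) is the same size as 40% positivity with 25% excluded, so EE loss is partly bracketed, though for the unstratified test. The word *ensure* follows a sentence that speaks of expectation, so that point is minor.

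**Conclusion.** The concern holds. With 60 patients and the plan's own effect size, the planned primary test has about 69–70% power at alpha 0.05 and about 80% at alpha 0.10, against the stated 74% and 83%. The shortfall against the stated figures is 4 to 5 points and about 3 points respectively, or about 6 stool-positive patients (6/0.40 = 15 enrolled). Full balance within strata would leave about 71–72%, still short.

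The conclusion rests on one exponential curve per arm, as the plan assumes, and on the assumed strata mix. It is a mismatch between sections of the plan, and the stated figures are correct for the test they list. The plan already accepts power below 80% at alpha 0.05, and no decision is shown to depend on the difference. The EE allowance and the guarantee of 60 positives are side points; the main finding does not need them.

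**What to change.** In SAP 4.1, Protocol 12.2 and the protocol synopsis:

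- State that the log-rank test is stratified by age group and sex. Give the assumed share in each stratum, and restate power as about 70% at alpha 0.05 and about 80% at alpha 0.10 for 60 EE patients.
- Rerun the SAP sensitivity table with the stratified test and report the number of replicates. This also rechecks the last 61% cell.
- Preferably add rows for EE exclusion, for example 5%, 10% and 20%, labelled as assumptions.
- Replace the wording that guarantees 60 positives with an expected count of about 60 (90% range 50 to 70).

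The stratified primary test and the planned Cox model stay as they are. The cost is a text change and a rerun of an existing simulation, and a stated power 4 to 5 points less favourable. No extra patients are needed.

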4.2. Randomization, Stratification, and Blinding

Subjects will be randomized to the niclosamide plus SoC or placebo plus SoC arms using a computer-generated randomization list generated by the PPD unblinded randomization team and using an IWRS. The treatment assignment is performed by pre-assigning the subject's number to the treatment kits corresponding to the randomization list.

Subjects will be randomized for Part 1 of the study in a 2:1 ratio to niclosamide plus SoC or placebo plus SoC. Subjects will be randomized for Part 2 of the study in a 1:1 ratio to

niclosamide plus SoC or placebo plus SoC and balanced and stratified by age (<65 years, ≥65 years) and sex (Female, Male).

This study will be double-blinded, meaning that the subjects, investigators, and site staff will be blinded to the subject treatment assignments until the completion of the long-term follow-up at Month 6. Any member of the study team involved in study conduct or participation in data handling decisions will also be blinded to the subject treatment assignments, but only until the completion of the short-term follow-up at Day 43.

At the initiation of the study, the study site will be given instructions on the method for breaking the blind. The method for breaking the blind will use the IWRS process. Unblinding of individual subject treatment by the Investigator should be limited to medical emergencies or urgent clinical situations in which knowledge of the subject's study treatment is necessary for clinical management. In such cases, the Investigator must first attempt to contact the PPD Medical Monitor to discuss and agree to the need for unblinding. In situations which the Investigator has attempted and failed to contact the PPD Medical Monitor and/or the urgency of the case requires immediate action, investigators should use their best judgment, based on the nature and urgency of the clinical situation, and proceed with unblinding.

Once a subject's treatment assignment has been unblinded for a medical emergency or urgent clinical situation, the PPD Medical Monitor should be notified within 24 hours of unblinding of the treatment. Information relating to unblinding (e.g., the reason, date) should be clearly recorded in the subject's study file.

4.3. Analysis Sets

4.3.1. Full Analysis Set (FAS)

The full analysis set (FAS) will consist of all randomized subjects who received at least one dose of study drug. The FAS will be used for systemic and respiratory efficacy secondary endpoints as well as exploratory endpoints and will be analyzed according to the study treatment as randomized.

4.3.2. Efficacy Evaluable (EE) Set

The efficacy evaluable (EE) set will consist of all randomized subjects who received at least one dose of study drug, had a positive stool test for SARS-CoV-2 on Day 1 assessed by RT-PCR, and did not test positive for bacteria or parasites in the screening stool analysis by the local laboratory. The EE set will be used for the primary efficacy endpoint and relevant gastrointestinal efficacy secondary endpoints and will be analyzed according to the study treatment as randomized.

4.3.3. Per Protocol (PP) Set

The per-protocol (PP) set will consist of subjects in the evaluable efficacy set who had at least 80% exposure of study drug (i.e., at least 12 days with any dose administered) and do not have major protocol deviations that may affect the primary efficacy endpoint (time to fecal viral RNA

clearance). The PP set will be used as a supportive analysis set for gastrointestinal efficacy analyses and will be analyzed according to the study treatment as randomized.

4.3.4. Safety (SAF) Set

The safety (SAF) set will include all randomized subjects who received at least one dose of study drug. The SAF set will be used for safety summaries and will be analyzed according to the study treatment actually received.

5. Subject Disposition

Subject disposition will be presented separately for Part 1 and Part 2 of the study.

5.1. Disposition

Subject disposition will be summarized by treatment group and overall for all subjects who provided informed consent and were screened. The subject disposition summary includes the number and percentage of subjects for the following categories: screened, randomized, treated, completed study treatment and discontinued study treatment, completed Day 43 follow-up visit and discontinued before Day 43 follow-up visit. The reasons for discontinuation of study treatment and discontinuation before Day 43 follow-up visit will be summarized in this table. In addition, reasons for screen failures will also be summarized overall. All percentages will be based on the number of subjects randomized, except for screen failures.

For subjects who completed Day 43 follow-up visit, a separate disposition summary will be provided to present the number and percentages of subjects who completed the long-term follow-up and subjects who discontinued from the long-term follow-up and reasons for discontinuation.

Study drug completion data will be collected on the End of Treatment eCRF. Disposition data for randomized subjects will be collected on the End of Study Day 43 and the End of Long Term Follow Up eCRFs. For screen failures, reasons will be collected on the Inclusion Exclusion eCRF or End of Study Day 43 eCRF.

Additionally, a summary of the analysis sets will be provided to include the number and percentage of subjects in each analysis set (FAS, EE, PP, and SAF) by treatment group and overall. The number and percentage of subjects excluded from each analysis set and the reasons for exclusion will also be presented. All percentages will be based on the number of subjects randomized.

Subject disposition and exclusions from analysis sets will also be presented in a listing.

